## 835 G4 Missing Outcome Data

All attempts will be made using Good Clinical Practice and through the reduction of the complexity and number of assessments to minimize the occurrence of missing outcome data. It will be assumed that all missing data will be at random. As this is a small pilot study, no computational techniques will be employed to adjust analyses for missing data.

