### 542 Gabapentin Study Flow Chart

549	
550	
551	
552	
553	
554	a. Federal guidelines require timely reporting (within 15 calendar days) of an
555	unanticipated or life-threatening event or death occurring within 30 days of
556	active study participation.
557	
558	
559	Titration Period: maximum duration 4 weeks
560	
561	Placebo. In this study, we plan to use an inert placebo and not an active drug
562	or non-active drug with side effects similar to gabapentin. Participants randomized to the
563	Placebo arm will participate in a 4-week Titration Period. Placebo will be supplied to
564	patients in opaque capsules in blinded fashion. The medications will be distributed in 4
565	separate vials representing each of the four weeks of the Titration Period. If intolerable
566	adverse reactions occur, the dosage will be decreased to prior tolerable dose.
567	Gabapentin. Participants randomized to the gabapentin arm will take
568	gradually titrated dosages of gabapentin as follows:
569	
570	Week 1, 900 mg/d (300 mg TID)
571	Week 2, 1800 mg/d (600 mg TID)
572	Week 3, 2700 mg/d (900 mg TID)
573	Week 4, 3600 mg/d (1200 mg TID)
574	
575	Gabapentin (300 mg per capsule) will be supplied to participants in opaque
576	capsules in blinded fashion identical to the supply of Placebo. The medications will be
577	distributed in 4 separate vials representing each of the four weeks of the Titration Period.
578	All participants' dosages will be titrated to a maximum dose of 3600 mg/d, regardless of
579	any effect achieved at lower dosages. If intolerable effects occur, dosage will be
580	decreased by 1 dose (300 mg) step (e. g. if 2700 mg/d is intolerable, dosage will be
581	decreased to 2400 mg/d). Further de-escalation will be determined by PI clinical
582	judgement to prior tolerable dose. Participants with intolerable effects may have a lower
583	maximum dose than 3600mg/d and may complete the Titration Period in less than 4
584	weeks. The dose established during the Titration Period will be maintained throughout
585	the Fixed-Dose period.

WEEK 1	WEEK 2	WEEK 3	WEEK 4
900 MG	1800 MG	2700 MG	3600 MG
1 MORNING 1 NOON 1 NIGHT (21 PILLS)	2 MORNING 2 NOON 2 NIGHT (42 PILLS)	3 MORNING 3 NOON 3 NIGHT (63 PILLS)	4 MORNING 4 NOON 4 NIGHT (84 PILLS)

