### 794 G1 Sample Size Determination and Power

795 To date there have been no studies investigating efficacy of gabapentin in COVID-19 796 related olfactory dysfunction. Due to the lack of preliminary data and effect size, 797 estimates of the sample size for this study will be determined based on feasibility. For 798 this pilot study, we plan to enroll 60 subjects. The sample size of 60 subjects is feasible 799 given the incidence of COVID-19 cases in Missouri and considering a conservative 800 estimate of a 10% rate of permanent olfactory dysfunction among those (~50%) who 801 experience olfactory dysfunction as one of the presenting symptoms. Using a 33% drop 802 out rate, we estimate that the sample size of 60 subjects randomized in a balanced way 803 between the two treatment groups will provide us with 40 evaluable cases. A previous 804 study exploring a different treatment for COVID-19 related anosmia in our lab showed 805 that 30% of the participants randomized to placebo reported improvement at the end of 806 the trial as compared to baseline. We aim to observe a 25% difference in the response 807 rate between gabapentin and placebo groups. Assuming that this will be the response rate 808 in the placebo group of our trial, the sample size of 20 subjects per group will provide us 809 with a 95% Confidence Interval -5% to 55% around the desired proportion difference of 810 25% between gabapentin and placebo groups.

811

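### G4 assumes outcomes are missing at random and bars any adjustment, so with 33% loss planned the CGI-I responder comparison is in effect an untested completer analysis

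*Combined protocol and SAP*

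**What the plan says.** - **G4 (Missing Outcome Data)** undertakes to keep missing data to a minimum, then says "It will be assumed that all missing data will be at random" and "As this is a small pilot study, no computational techniques will be employed to adjust analyses for missing data".
- **G1 (Sample Size)** gives the scale: "this pilot study, we plan to enroll 60 subjects", a loss of 33%, and a balanced randomisation that "between the two treatment groups will provide us with 40 evaluable cases". Its precision statement uses 20 per group.
- **E2, 2.h** says that data gathered before withdrawal are left out of the analysis.
- **G3** calls the primary analysis intention-to-treat and compares responder rates by Fisher's exact test. **C3** divides responders by the number of participants in each group. Neither says how a participant with no rating is scored.
- **F2 and F4** collect no forms at the end of titration. The first CGI-I comes after the 8-week Fixed-Dose period.
- **E2, 2.g** provides an exit interview on adverse effects and the reason for leaving, but it does not mention a CGI-I rating.
- **E3, 3.f** has the only sensitivity analysis mentioned. It is optional and concerns prior or current therapies.

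**The concern.** The stated assumption and the stated method do not match. Missing at random allows loss to depend on observed data, such as side effects or baseline severity. If those data also predict response, a plain comparison of responder rates among completers is biased unless the analysis uses them, and G4 rules that out. For the unadjusted Fisher comparison to be unbiased, missingness must be unrelated to response within each arm.

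Loss related to treatment is plausible here. The placebo is inert and is not meant to mimic gabapentin's side effects (F2). Participants with serious adverse effects are removed (F3, 3.a). Anyone who leaves before the end of the Fixed-Dose period has no CGI-I rating at all. If those who leave the gabapentin arm are mostly people who felt no benefit, the observed response rate in that arm rises even when the drug does nothing, and no planned analysis would show it. The result matters beyond this trial, because D3 and 2.e say it is to be used to initiate a larger one.

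**Working it through.** **Inputs from the documents.** 60 enrolled, 33% loss, 40 evaluable, placebo response 30%, target difference 25 points (all G1); 1:1 allocation (E3, 3.c).

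**Assumptions not in the documents.** Losses split 10 and 10 between arms; the response rates among those without a rating; the strength of any link between response and dropout.

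**1. The plan's own figures.** 60 × (1 − 0.33) = 40.2, so 40 evaluable, 20 per arm. At 55% versus 30% this is 11/20 versus 6/20. The Wald 95% CI is 0.25 ± 1.96 × √(0.55×0.45/20 + 0.30×0.70/20) = 0.25 ± 1.96 × 0.151, or −4.6% to 54.6%. This matches the −5% to 55% in G1, so the planned precision is that of a completer analysis.

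**2. All 30 randomised per arm.** With response rates g and p among the 10 missing on gabapentin and on placebo, the difference is [(11 + 10g) − (6 + 10p)] / 30.

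- All missing are non-responders: 11/30 − 6/30 = +16.7 points (95% CI −5.7 to 39.1).
- Missing gabapentin 0%, missing placebo 30%: 11/30 − 9/30 = +6.7 points (95% CI −17.1 to 30.5).
- Lower bound: 11/30 − 16/30 = −16.7 points.
- Upper bound: 21/30 − 6/30 = +50.0 points.

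The same formula over a grid of rates gives, in points:

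| Missing gabapentin | Placebo 0% | Placebo 30% | Placebo 55% | Placebo 100% |
|---|---|---|---|---|
| 0% | +16.7 | +6.7 | −1.7 | −16.7 |
| 30% | +26.7 | +16.7 | +8.3 | −6.7 |
| 55% | +35.0 | +25.0 | +16.7 | +1.7 |
| 100% | +50.0 | +40.0 | +31.7 | +16.7 |

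**3. Where the benefit disappears.** Setting the formula to zero gives p − g = 5/10, a contrast of 50 points. Of the 11 × 11 = 121 possible pairs of missing-responder counts, 100 keep the sign, 6 give zero and 15 reverse it. In general the tipping contrast is twice the observed difference: 20 points at an observed +10, and 10 points at +5.

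**4. Unequal loss.** With 15 lost on gabapentin and 5 on placebo, at the same observed rates, the bounds are −14.2 to +52.5 points. The all-non-responder difference is 0.55×15/30 − 0.30×25/30 = +2.5 points.

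**5. No true effect (30% in both arms), with placebo loss unrelated to response.** The error rates below come from exact enumeration with 20 per arm. They are the chance of a two-sided Fisher p ≤ 0.05 in gabapentin's favour.

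- No dropout bias, 30% versus 30%: 1.2%.
- Gabapentin non-responders have three times the odds of dropping out, with one third lost overall. Dropout is then 18.1% in responders and 39.9% in non-responders (0.30×0.181 + 0.70×0.399 = 0.333). The observed rate is 0.30×0.819/0.667 = 36.9%, a spurious difference of about +7 points; error 3.7%.
- Extreme case, all 10 lost on gabapentin are non-responders: 9/20 = 45% versus 30%, a spurious +15 points; error 10.1%.

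**The case against.** **The plan works against side-effect dropout.** F2 says "All participants' dosages will be titrated to a maximum dose of 3600 mg/d, regardless of" any effect seen at lower doses, but it goes straight on to allow a reduction for intolerable effects. D3 and E3, 3.b do the same, although the sections differ on the size of the step and need reconciling. Two-weekly check-ins (3.e) also support retention. This stands: step-down may reduce the loss, and no figure in the documents shows that differential dropout is likely. It does not cover participants removed for serious adverse effects or those who withdraw anyway.

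**The sign is not really in doubt at the planned result.** A reader might infer from the bounds that the direction of the result is decided by people who gave no rating. The documents do not support that at +25 points, where reversal needs a contrast above 50 points. Any trial with a third missing has wide worst-case bounds, and the completer interval already includes zero. This stands for the planned result. It is weaker for a smaller observed difference.

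**The large error rate needs an extreme assumption.** This stands. The 10.1% requires every lost gabapentin participant to be a non-responder; the milder case gives 3.7%.

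**This partly repeats the clash between 2.h and intention-to-treat.** Read literally, C3 and G3 keep everyone in the denominator, and under no effect the active arm would be 9/30 rather than 9/20. The overlap is real. But settling who is counted does not say how a missing rating is scored, nor how far the result depends on that choice.

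**Missing at random does not automatically bias an unadjusted comparison, and G4 may mean completely at random.** The first part is correct: there is bias only if the predictors of dropout also relate to response. On the second, the looser reading would match the method, but it is a stronger assumption and equally untested.

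**Conclusion.** The point holds as a gap between assumption and method in G4, with no sensitivity analysis to test it. At the planned result the realistic consequence is shrinkage, from +25 points to between about +7 and +17 under the two scenarios in which missing gabapentin participants do not respond. It does not follow that the sign is unsettled, that treatment-related dropout is likely, or that a false positive rate near 10% should be expected. Those readings need contrasts or dropout patterns for which the documents give no evidence. Under no true effect and a moderate link between non-response and dropout, the spurious difference is about 7 points.

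The sizes rest on an equal 10/10 loss and on assumed response rates among those without a rating. The point concerns CGI-I only; the UPSIT mixed model can use partial data under missing at random, although 2.h would exclude withdrawn participants there too. The small pilot size may excuse multiple imputation. It does not excuse leaving out a table that needs only arithmetic, since efficacy is the primary aim and a test is run. The change should be made.

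**What to change.** In G4, replace the bar on adjustment with three items:

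1. A rule for how a randomised participant without a CGI-I rating is counted in the primary analysis, reconciled with the denominator in C3, the exclusion in 2.h and the intention-to-treat statement in G3.
2. Missing CGI-I counts by arm, with reasons. The exit interview in 2.g already collects the reason for leaving.
3. A pre-specified sensitivity table giving the arm difference and 95% CI with missing gabapentin and missing placebo participants each assigned response rates of 0%, 30%, 55% and 100%. The 0%/0% cell is the all-non-responder case. The conclusion should state at which assumptions the estimated benefit disappears.

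No fixed robustness threshold is needed; any single cell chosen as a pass mark would be arbitrary. No imputation software is required. The cost is one paragraph and one extra results table, and the headline may look less favourable.

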## 840 G5 Unblinding Procedures

841 The blind will be broken for individual participants for safety concerns. Knowledge of

- 842 the treatment received is necessary for interpreting the event, may be essential for the 843 medical management of the subject, and may provide critical safety information about
- gabapentin that could have implications for the ongoing conduct of the trial (e.g.,
- 845 monitoring, informed consent). For unblinding, the research coordinator will contact the
- research pharmacist and provide the study ID number for the participant to be unblinded.
- 847 The research pharmacist will contact the PI directly and reveal the intervention
- 848 assignment. The research coordinator will remain blinded.
- 849
- 850 H
- Data Handling and Record Keeping
- 851

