### 443 **2.g** When and How to Withdraw Subjects

444 A participant can withdraw consent for the study at any time. Participants will be allowed 445 to end participation in the study at any point should they desire. If a participant must be 446 withdrawn due to a drug-related serious adverse event, then blind will be broken and, if 447 on gabapentin, drug withdrawal will be tapered or completely stopped based on the 448 clinical judgement of the PI. All participants will have an exit interview to ascertain any 449 adverse effects and discuss the reason for ending participation. The study team will 450 follow them for safety reasons up to 30 days after stopping use of the study drug.

451

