### The specific monitoring plan for this study is based on the potential risk of participation

and size and complexity of the planned investigation. Based on these considerations, this

- study will have a monitoring committee comprised of [name], [name], and
- 654 [name], the study biostatistician. All reports of a Serious Adverse Event (SAE) or

- 655 an Unexpected Adverse Event (UAE) will be investigated by the monitoring team and 656 reported to Washington University HRPO according to the reporting requirements. 657 658 Participants who experience serious adverse effects with gabapentin therapy will be 659 removed from the study. Participants with serious adverse effects will be instructed to 660 call 911, seek immediate medical care and discontinue all further gabapentin treatment. If 661 tolerated, all participants will complete the Titration period ( $\leq 4$  weeks), Fixed-Dose 662 period (8 weeks), and Taper-Down period (2 weeks) for maximum 14 weeks of active participation. In addition, there will be a 4-week, post-Taper completion follow-up for 663 664 maximum total of 18-week trial duration.
- 665 **3.a Medical Monitoring**
- 666

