### 679 **3.b Definitions of Adverse Events**

Adverse event (AE) means any untoward medical occurrence associated with the use of a
drug in humans, whether or not considered drug related (21 CFR 312.32(a)).

682

An adverse event (also referred to as an adverse experience) can be any unfavorable and
unintended sign (e.g., an abnormal laboratory finding), symptom, or disease temporarily
associated with the use of a drug, without any judgment about causality or relationship to
the drug.

687

688 An adverse event can arise from any use of the drug (e.g., off-label use, use in 689 combination with another drug) and from any route of administration, formulation, or

- 690 dose, including an overdose.
- 691

692 Serious adverse events (SAEs) are special cases of an adverse event where adverse693 outcomes are severe. SAEs include the following events:

- 694 695
- Death of any of the participants associated with a clinical trial.
- An event which can lead to life-threatening complications or put the life of participants at risk as a result of participation in a clinical trial.

698 699	•	Events that result in such a condition where the participants may require immediate hospitalization or increase the duration of hospitalization.
700	•	Any events that lead to a permanent or temporary physical disability in the body
700	•	of the participants. Any sort of incapacity is also regarded as SAE.
702 703	•	Any events that lead to any type of congenital abnormalities. It also includes any cases of birth defects resulting from the clinical trials.
704 705 706	•	Any events where an investigator or team of investigators finds feel that it can lead to significant hazards.
707 708	Class	ification of Events
709	i	Relationship
710 711 712 713 714 715 716	relation the Al (e.g., 1 AEs, 1	E or SAE may or may not be causally related to the study intervention. A causal onship means that the intervention caused (or is reasonably likely to have caused) E. This usually implies a relationship in time between the intervention and the AE the AE occurred shortly after the participant received the intervention). For all t is the responsibility of the Principal Investigator who examines and evaluates the t to determine the relatedness of the event to the study intervention.
717	ii	Severity
718 719	Sever judgm	ity refers to the intensity of a specific event and is a matter of individual clinical ent.

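### Nothing requires the PI to record relatedness, severity and expectedness before learning the assignment, and the unblinding and removal wording differs between sections

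*Combined protocol and SAP*

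**What the plan says.** G5 states: "The blind will be broken for individual participants for safety concerns". It then gives three reasons. Knowledge of "the treatment received is necessary for interpreting the event" is the only one stated as definite; use in medical management and information for the conduct of the trial are stated as possible. On disclosure: "The research pharmacist will contact the PI directly and reveal the intervention" assignment. The research coordinator stays blinded.

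F3, 3.b (Classification of Events, Relationship) says that for all adverse events it "is the responsibility of the Principal Investigator who examines and evaluates the" participant "to determine the relatedness of the event to the study intervention". The same section leaves severity to individual clinical judgement and defines expectedness by comparison with the documented risk information.

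E2, 2.g says that if a participant must be "withdrawn due to a drug-related serious adverse event, then blind will be broken and, if" that participant is on gabapentin, the PI's judgement decides how the drug is withdrawn.

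F3, 3.a Safety and Compliance Monitoring says: "Participants who experience serious adverse effects with gabapentin therapy will be" taken out of the study. The next sentence tells participants with serious adverse effects, with no arm named, to "call 911, seek immediate medical care and discontinue all further gabapentin treatment".

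F3, 3.a Medical Monitoring (Investigator only) provides for contacting the pharmacist after a serious or unexpected adverse event when the code has to be opened. Any participant unblinded in this way is removed.

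**The concern.** Whether an event was caused by the study drug is a judgement, and a judge who knows the arm may answer differently for the same event. Here the person who judges is the person who is told, and helping to interpret the event is a stated purpose of telling. If relatedness is entered after the reveal, being called related can become partly a proxy for being on gabapentin. The placebo arm then loses some of its value as a comparator for attributed events. The secondary aim (C2) is to describe the adverse effects of gabapentin, with all participants monitored, so this is where any damage would fall.

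The differing triggers add to the problem. Staff who follow one section would open the code in situations where staff who follow another would not. The gabapentin-only removal sentence cannot be applied literally by staff who do not know the assignment.

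**Working it through.** The point concerns procedure, and the plan states no figure to reproduce. The check is to set the provisions side by side.

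**Order of judgement and reveal**
- E2, 2.g: the event is already called drug-related when the blind is broken. This implies judgement first, but does not require it to be recorded then.
- G5: the assignment is needed to interpret the event. This implies reveal first, or at least allows it.
- F3, 3.b: the PI decides relatedness. Nothing is said about timing relative to a code break, or about being blinded when deciding.
- F3, 3.c (data collection): the coordinator abstracts events from source documents. The coordinator stays blinded but is not given the relatedness decision.

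An investigator who learns the assignment and only then enters relatedness, severity and expectedness has breached none of these provisions.

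**Trigger for breaking the blind**
- E2, 2.g: withdrawal because of a serious event judged drug-related.
- F3, 3.a Medical Monitoring: a serious or unexpected event where unblinding is needed, with no criterion for need.
- G5: safety concerns, with no threshold of seriousness or need.

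These run from narrow to broad. An unexpected non-serious event, for example, could lead to a code break under the second and third but not under the first.

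**Removal**
- F3, 3.a Safety and Compliance Monitoring: tied to serious effects on gabapentin.
- F3, 3.a Medical Monitoring: any participant unblinded for a serious or unexpected event, in either arm.
- E2, 2.g: the trigger names no arm. The gabapentin condition governs only how the drug is withdrawn.

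The first is out of line with the other two.

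**Scale of one event**
G1 plans 60 subjects allocated 1:1, so 60/2 = 30 per arm, with 40 evaluable, so 40/2 = 20 per arm. If each participant counts once, a change in the classification of one participant's event moves that arm's related-event rate by
- 1/30 = 3.3 percentage points with 30 per arm;
- 1/20 = 5 percentage points with 20 per arm.

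This is the effect of one change, not a forecast. The documents give no expected number of serious events and no figure for how often attribution would change.

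**The case against.** The strongest reply is that the sections can be read together. Section 2.g places the drug-related judgement before the code break, Medical Monitoring limits unblinding to cases that need it, and a monitoring team investigates all serious and unexpected event reports. Interpreting an event in G5 need not mean deciding causality. G3 plans no comparison of related events by arm, and adverse events are defined and captured regardless of cause, so all-cause counts do not depend on attribution.

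Much of this stands. It limits the consequence to attributed events and to the PI's other graded judgements. It does not remove the gap: the order in 2.g is an implication, G5 points the other way, and the monitoring team's review is not described as blinded or as replacing the PI's decision. Breaking the blind for a participant's care is not itself a flaw.

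A reader might infer more than the documents support:
- *That serious-event handling as a whole is unblinded, or that a placebo participant with the same event is not covered.* This takes one sentence of F3, 3.a in isolation. Section 2.g and Medical Monitoring apply to both arms, and the gabapentin-only wording may simply be loose drafting.
- *That relatedness by arm is itself the secondary aim.* C2 speaks of describing adverse effects and does not mention relatedness.
- *That the primary outcome is compromised.* CGI-I is rated by the participant, and participants unblinded under Medical Monitoring are removed. No route is shown from the PI's knowledge of one participant's arm to anyone's rating. The exclusion of withdrawn participants' data in 2.h, set against intention-to-treat in G3, is a separate matter.

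**Conclusion.** The point holds as a gap in documentation and a conflict of wording. The plan allows relatedness, severity and expectedness to be entered by a PI who already knows the assignment, and gives interpretation of the event as a reason for that knowledge. Attribution may therefore differ by arm; the documents do not show that it will. The size is unknown. It depends on how many events lead to a code break and on how often knowledge of the arm would change the judgement, and the plan states neither. All-cause adverse event counts by arm are not affected by attribution.

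The unblinding triggers and the removal wording also need to be reconciled. This review takes no view on which removal or drug-withdrawal rule is right. Overall this is a cheap improvement. It is worth making before the first code break, because a judgement made after the reveal cannot be made blind again.

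**What to change.** 1. In G5 and F3, 3.b, require the PI to make a time-stamped REDCap entry of severity, relatedness and expectedness before the pharmacist is contacted for any non-urgent code break.
2. State that urgent care is never delayed for this entry. Where the code is opened first, flag the entry as made after unblinding.
3. Use the pre-reveal judgement in any by-arm description of related events, and record later revisions separately. Report flagged entries as such.
4. Reconcile the unblinding triggers and the removal wording in E2 2.g, both 3.a subsections of F3, and G5, so that staff can apply them without knowing the assignment. The choice of rule belongs to the investigators.

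The cost is wording in these sections and one time-stamped form. The downside is one extra step before a non-urgent code break.
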